4.1.5 Exploratory objectives and endpoints

Exploratory Objectives	Exploratory endpoints
To determine whether acetazolamide compared with placebo in combination with loop diuretics will have an effect on body weight.	Change in body weight.
To determine whether acetazolamide compared with placebo in combination with loop diuretics will reduce the incidence of all cause rehospitalisation's.	All cause rehospitalisation during first 3 months after study start dose.
To determine whether acetazolamide compared with placebo in combination with loop diuretics will have an effect on total urinary volume and natriuresis.	Total urinary volume and natriuresis starting from first intravenous (IV) diuretic administration at randomization until the morning of day 3.
To determine whether acetazolamide compared with placebo in combination with loop diuretics will have an effect on plasma natriuretic peptides.	Change in plasma natriuretic peptides change from screening until day 4 or at discharge (whatever comes first) and at 3 months follow up visit.
To determine whether acetazolamide compared with placebo in combination with loop diuretics will have an effect on the total dose of IV loop diuretics used during first 4 days.	Total dose of IV loop diuretics used during first 4 days.
Effect of decongestion on uptitration of neurohormonal blockers	Changes in doses of neurohumoral blockers.
To determine whether acetazolamide compared with placebo in combination with loop diuretics will reduce the need for renal replacement therapy.	Need for renal replacement therapy or ultrafiltration during first 3 months after study start dose.
To determine whether acetazolamide compared with placebo in combination with loop diuretics will reduce the incidence of hyponatremia during treatment phase.	Hyponatremia during treatment phase.
To evaluate if liver dysfunction at screening has an effect on the treatment effect on the primary endpoint.	Liver dysfunction at screening and primary endpoint.
To determine whether acetazolamide compared with placebo in combination with loop diuretics will have an effect on plasma volume changes during treatment phase.	Change in plasma volume during treatment phase (assessed by albumin and hematocrit)

Exploratory Objectives	Exploratory endpoints
To evaluate if iron deficiency at screening has an effect on the treatment effect on the primary endpoint	Iron deficiency at screening and primary endpoint
To determine whether acetazolamide compared with placebo in combination with loop diuretics will have an effect on congestion score during the study.	Changes in congestion score (total and each subscore) during treatment phase and 3 months of FU.
To determine whether acetazolamide compared with placebo in combination with loop diuretics will have an effect on EQ-VAS score during the study.	Changes in EQ-VAS score during treatment phase and 3 months of FU.

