3.6 Exploratory tertiary endpoints

1. Body weight change after day 1, 2, 3, 4 and discharge compared to screening
2. All-cause mortality during first 3 months after study start dose
3. Heart failure readmissions during first 3 months after study start dose
4. All cause rehospitalisation during first 3 months after study start dose
5. Total urinary volume and natriuresis starting from first intravenous (IV) diuretic administration at randomization until the morning of day 3
6. Relative plasma BNP or NT-proBNP change from screening until day 4 or at discharge (whatever comes first) and at 3 months follow up visit
7. Total dose of IV loop diuretics used during first 4 days
8. Changes in doses of neurohumoral blockers from baseline to discharge and after 3 months.
9. Need for renal replacement therapy or ultrafiltration during first 3 months after study start dose
10. Hyponatremia during treatment phase
11. Hypokalaemia during treatment phase
12. Incidence of metabolic acidosis requiring NaHCO₃ supplements during first 4 days
13. WRF defined as a >0.3 mg/dL increase in serum Cr, or a >20% decrease in eGFR by the CKD-EPI formula during treatment phase
14. Liver dysfunction at screening
15. plasma volume changes during treatment phase (assessed by albumin and hematocrit)
16. Occurrence of iron deficiency at screening
17. Optional laboratory sub-study in participating centers: Change from screening in selected biomarkers from baseline through 3 months after study start dose in a subset of randomized patients

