7.7 Treatment phase assessments

7.7.1 Day 1

- Request patient to empty their bladder before administration of the first dose of loop diuretics.
- Administer the first bolus of loop diuretics and acetazolamide or placebo to the patient.
- Start the urinary collection immediately after first bolus of loop diuretics and acetazolamide or placebo is administered. The collection will stop the latest as close to but prior to the morning bolus of study medication on day 3. Urinary catheter insertion is strongly recommended but not mandatory to achieve an optimal urine collection. However, in case of urinary incontinence, placement of a urinary catheter is mandatory. Care should be taken to ensure ALL urine is collected. For more details regarding the study urinary collection see [appendix 4](#).

If the patient is enrolled between midnight and 6 a.m., day 1 assessments and day 2 assessment can be performed on the same day but only if there is a difference of minimum 6 hours between the start of the study medication on day 1 and study medication on day 2.

7.7.2 Day 2, Day 3 and Day 4

- Collect vital signs including body weight, arterial blood pressure, heart rate
- As long as patient is assessed as volume overloaded during the previous volume assessment, perform volume assessment by the Principal Investigator or a Sub-investigator who has been trained in the study volume assessment (Figure 3 in section 8)
- Collect morning blood sample for local laboratory assessment: serum haemoglobin, haematocrit, electrolytes (Na, K, Cl, HCO₃), serum urea, serum Cr, serum albumin.
- On the morning of Day 2 and Day 3, collect an urine sample from urine collection period 1 and period 2 respectively for analysis in local lab. In case patient is participating in the optional laboratory sub-study, collect an additional urine sample for each urine collection period for shipment to the University Biobank Limburg for storage and additional research (see [section 7.10](#)). Urinary collection will stop at the morning of day 3 ([appendix 4](#)).
- In case patient is still volume overloaded continue study treatment as described in [section 8](#)
- Collect concomitant medication ([see Appendix 5](#))
- Document and assess adverse events ([section 9](#))
- In addition, on the morning of day 4 or at discharge (whatever comes first):
 - EQ-5D to be completed by the patient.

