4 STUDY SYNOPSIS

The ADVOR study is a phase IV randomized, multicentre, double-blind study, comparing monotherapy with high-dose loop diuretics (standard of care - SOC) versus combination therapy with acetazolamide and high-dose loop diuretics in patients with decompensated heart failure (HF) and clinical signs of volume overload. For more details regarding the intervention see section 4.3

The study consists of 3 phases:

- **screening phase:** starting from identifying a study subject prior to / during hospitalization until the first dose of study medication will be given
- **treatment phase:** starting from the first dose of study medication administration until the morning of day 4 or earlier in case of successful decongestion prior to day 4.
- **follow-up phase:** starting when the treatment phase ends until 3 months after the study start dose.

[figure not shown]

Figure 1. Trial Flow Chart

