4.1.4 Safety objectives and endpoints

Safety Objective	Safety Endpoints
To evaluate the safety of the combination therapy with acetazolamide in this patient population.	
 - Severe metabolic acidosis at any time during study treatment - Doubling or more ($\geq 2x$) of baseline serum Creatinine, or $\geq 50\%$ decrease in baseline eGFR at any time during study treatment - Hypokalaemia at any time during study treatment - Hypotension at any time during study treatment

Definition of Safety endpoints

- Severe metabolic acidosis: a value of bicarbonate < 12 mmol/L at any time during study treatment (day 1- day 4)
- Worsening of eGFR or the need for renal replacement therapy during the index hospitalization. eGFR is obtained via the CKD-EPI formula. The eGFR values will be calculated (in mL/min/1.73 m²) from the local laboratory creatinine measurements using the CKD-EPI formula (Levey et al 2009)².
- Hypokalaemia: a value of potassium $\leq 3,0$ mmol/L at any time during study treatment (day 1- day 4)
- Hypotension: a value of systolic blood pressure < 85 mmHg at any time during study treatment (day 1- day 4)

Baseline laboratory value

For all laboratory variables, the baseline value is defined as the last value prior to the first dose of study drug.

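### Hyponatraemia, and in the protocol also hypokalaemia and worsening renal function, is counted over a treatment phase that ends early at decongestion, which slightly favours the arm that decongests faster

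*Combined protocol and SAP*

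**What the plan says.** **Definition of the phase.** SAP v2.0 section 4 runs the treatment phase from the first dose "until the morning of day 4 or earlier in case of successful decongestion prior to day 4". Protocol v2.0 section 4 says the same in substance. SAP section 4.1.2 makes decongestion on the morning of day 2 or day 3 a primary success.

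**Endpoints tied to that phase.** SAP section 4.1.5 asks whether acetazolamide "will reduce the incidence of hyponatremia during treatment phase". Protocol section 3.6 lists hyponatraemia, "Hypokalaemia during treatment phase", and worsening renal function, defined by a creatinine rise or a "decrease in eGFR by the CKD-EPI formula during treatment phase".

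**Endpoints with other windows.** Protocol section 3.6 counts metabolic acidosis requiring bicarbonate "supplements during first 4 days". In SAP section 4.1.4 the definitions for bicarbonate, potassium and systolic pressure read "at any time during study treatment (day 1- day 4". The renal safety endpoint is tied to study treatment in the table of that section, but to the index admission in the definition below it.

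**Sampling.** Protocol section 7.7.2 has sites "Collect morning blood sample for local laboratory assessment" on days 2, 3 and 4 without any condition on congestion. Only the volume assessment stops once the patient is dry. The footnotes to protocol section 7.9 move the day 4 assessments to discharge if that is earlier.

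**The concern.** An incidence is comparable between arms when both are counted over the same window. Here the window closes at an event that is itself a form of the primary success and that the trial expects to be more frequent with acetazolamide. A patient who is dry on day 2 contributes one post-dose morning sample to the count, whereas a patient who stays congested contributes three. With no true difference in risk, the arm with more early successes records fewer events.

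The hyponatraemia objective is worded as a reduction, so the artefact runs in the direction of the hypothesis. Neither document gives a person-time or fixed-window rule to offset it. What is at stake is the credibility of a favourable result on these secondary laboratory outcomes, not the primary conclusion.

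**Working it through.** **Inputs from the documents.** Success rates of 15% (control) and 25% (acetazolamide), 1:1 allocation, 519 patients (SAP sections 4.3.4 and 4.5). Three scheduled post-dose mornings: days 2, 3 and 4 (protocol section 7.7.2).

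**The plan's own figure.** The documents give no figure for hyponatraemia or for observation time. The two success rates are those behind the sample size: (1.96 + 0.8416)² × (0.15 × 0.85 + 0.25 × 0.75) / 0.10² = 247.24 per arm, consistent with the stated total of 494. Then 494 × 1.05 = 518.7, giving 519.

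**Assumptions, because the documents are silent.** The risk h of an event at each morning sample is the same in both arms and independent across mornings; h ranges from 1% to 10%. The day on which successes become dry is varied. The sample on the morning the patient is found dry is counted. Every patient dry on day 2 or 3 is a primary success, so at the planned rates the early share cannot exceed 15% and 25%.

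**Formula.** A patient with k counted samples has an event with probability 1 − (1 − h)^k, where k = 1, 2 or 3 for patients first dry on day 2, 3 or 4, and k = 3 for those never dry.

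At h = 5% the probabilities are 5.00%, 9.75% and 14.26% for k = 1, 2 and 3. If all successes fall on day 2:
- control: 0.85 × 14.26% + 0.15 × 5.00% = 12.9%
- acetazolamide: 0.75 × 14.26% + 0.25 × 5.00% = 12.0% (11.95% before rounding)

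| Timing of successes | Samples per patient, control vs acetazolamide | Incidence at h = 5% | Ratio |
|---|---|---|---|
| All on day 2 | 2.70 vs 2.50 | 12.9% vs 12.0% | 0.93 |
| Spread evenly over days 2 to 4 | 2.85 vs 2.75 | 13.6% vs 13.1% | 0.97 |
| All on day 4 | 3.00 vs 3.00 | 14.3% vs 14.3% | 1.00 |

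The ratios barely move with h: for all successes on day 2 they run from 0.926 (h = 1%) to 0.930 (h = 10%). At h = 5% the absolute differences are 0.93 and 0.46 percentage points. With about 259 patients per arm this is 0.0093 × 259 = 2.4 and 0.0046 × 259 = 1.2 patients.

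**Effect on a test.** With 259 per arm and equal true risk, the chance of a significant result in favour of acetazolamide is 2.9% to 6.6% across the scenarios with early decongestion, against a nominal 2.5%.

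**Sensitivity to one assumption.** If the sample on the morning of decongestion is also left out, the all-on-day-2 extreme becomes 0.85 × 3 = 2.55 against 0.75 × 3 = 2.25 samples, a ratio of 0.88.

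**After a fixed window.** With full sampling the ratio is 1.00. Protocol section 8.1 allows discharge 24 hours after decongestion, so some patients dry on day 2 may miss the day 4 sample. If all of them leave on day 3, the ratio is about 0.97 when every success falls on day 2 and about 0.99 when successes are spread evenly.

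**The case against.** The best defence is that the term is not used in one sense. The schedule in protocol section 7.9 places days 1 to 4 under the treatment phase for every patient. SAP section 4.3.3 lists the end of the phase, at most 4 days, and complete decongestion as separate times. Protocol Appendix 5 treats day 4 recording as part of the phase. On that usage the window is fixed and there is no bias. This stands as evidence of ambiguity, but the formal definition in both documents says otherwise, and an analyst would be entitled to follow it.

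Three stronger readings are tempting and are not supported.

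- *That all laboratory outcomes are affected.* Acidosis in the protocol has a fixed window, and the SAP safety endpoints for potassium, bicarbonate and blood pressure carry the day 1 to day 4 gloss. Plasma volume change shares the phase wording but is a change measure, so the incidence argument does not apply to it.
- *That early responders are observed for less time.* Blood sampling continues to day 4 or discharge. It is the counting rule that is short.
- *That acetazolamide must show fewer events by construction.* The window pushes counts in that direction only if successes come before day 4, and a higher true risk under acetazolamide could outweigh it. Fewer events because treatment really was shorter would be a genuine effect, not an artefact.

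It is also fair that the size rests on assumed timing and risk. Serial values in one patient are likely to be correlated, which would shrink the effect. Assuming, say, 12% dry on day 2 and 16% on day 3 with acetazolamide would imply 28% early successes, above the planned total of 25%. Finally, SAP section 5.3 classes every endpoint other than the primary as exploratory.

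**Conclusion.** The point holds as a minor one. Under the formal definition, the window for hyponatraemia (SAP section 4.1.5 and protocol section 3.6) and for hypokalaemia and worsening renal function (protocol section 3.6) depends on the primary outcome and leaves out samples that are collected anyway. At the planned success rates, with equal and independent per-sample risk and the decongestion-morning sample counted, the bias favours acetazolamide by about 0 to 7% relative. The upper end needs every success to fall on day 2. The primary test and the sample size are unaffected.

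In SAP section 4.1.4 the day 1 to day 4 gloss largely protects potassium, bicarbonate and blood pressure. It nevertheless conflicts with the words about study treatment for patients who stop early, since SAP section 4.3 stops study medication once the patient is dry. The renal safety endpoint has two windows that cannot both apply.

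**What to change.** In protocol section 3.6 and SAP sections 4.1.4 and 4.1.5, state that these events are counted over all samples from the first dose to the morning of day 4, or to discharge if earlier, in every patient, whether or not study drug has been stopped. Apply the same window to the blood pressure readings. Choose one window for the renal safety endpoint and use it in both the table and the definition. Use the term treatment phase in one sense throughout.

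Report the number of counted samples per arm beside each incidence, because early discharge leaves a small imbalance that the wording cannot remove (ratio about 0.97 to 0.99 in the cases above). State the sodium threshold for hyponatraemia at the same time, since SAP section 4.1.5 gives none.

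The cost is wording only: the schedule already requires the samples, and no new data, patients or visits are needed.

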4.2 Patient population

4.2.1 Inclusion Criteria

- Signed written informed consent must be obtained before any study assessment is performed
- Male or female patients of 18 years of age or older
- An elective or emergency hospital admission with clinical diagnosis of decompensated HF with at least one clinical sign of volume overload (e.g. oedema (score 2 or more), ascites confirmed by echography or pleural effusion confirmed by chest X-ray or echography)
- Maintenance therapy with oral loop diuretics at a dose of at least 1 mg bumetanide or an equivalent dose for at least 1 month before hospital admission (Conversion: 1 mg bumetanide = 40 mg furosemide = 20 mg torsemide)
- Plasma NTproBNP levels >1000 ng/L or BNP levels >250 ng/L at the time of screening
- Assessed LVEF by any imaging technique; i.e. echocardiography, catheterization, nuclear scan or magnetic resonance imaging within 12 months of inclusion

4.2.2 Exclusion Criteria

- Concurrent diagnosis of an acute coronary syndrome defined as typical chest pain in addition to a troponin rise above the 99th percentile and electrocardiographic changes suggestive of cardiac ischemia
- History of congenital heart disease requiring surgical correction
- History of a cardiac transplantation and/or ventricular assist device
- Systolic blood pressure <90 mmHg or mean arterial pressure <65 mmHg at screening
- Expected use of intravenous inotropes, vasopressors or nitroprusside during the study. The use of nitrates and/or molsidomine is allowed at the discretion of the treating physician.
- Estimated glomerular filtration rate <20 mL/min/1.73m² at screening
- Use of renal replacement therapy or ultrafiltration at any time before study inclusion
- Treatment with intravenous loop diuretics > 2 mg bumetanide or an equivalence of another loop diuretic during the index hospitalization and prior to randomization
- Treatment with acetazolamide within 1 month prior to randomization
- Exposure to nephrotoxic agents (i.e. contrast dye) anticipated within the next 3 days
- Use of any non-protocol defined diuretic agent with the exception of mineralocorticoid

receptor antagonists during the treatment phase of the study. Thiazides, metolazone, indapamide and amiloride should be stopped upon study inclusion. If patient is taking a combination drug including a thiazide-type diuretic, the thiazide-type diuretic should be stopped.

- Current use of sodium-glucose transporter-2 inhibitors
- Subjects who are pregnant or breastfeeding
- Subjects with urinary incontinence who are not willing to receive a bladder catheter.

4.3 Intervention

At the moment of randomization, oral loop diuretics are stopped and the patient receives an IV bolus of loop diuretics at a dose equal to the double of his oral daily maintenance dose with a maximal dose of 5 mg bumetanide (=200 mg furosemide). Bumetanide is the preferred loop diuretic agent to be used in this trial. Between administering the start dose and next treatment dose a minimum of 6 hours is required. During the remaining part of the treatment phase, the patient will continue to receive 2 IV treatment doses every day provided that the treating physician has concluded during the morning rounds that the patient is still volume overloaded (see Figures 2, volume assessment score > 1). The IV loop diuretic dose will be the orally daily maintenance dose, administered between 8:00 and 12:00 am, together with an intravenous bolus of 500 mg of acetazolamide or placebo. The second dose of IV loop diuretics, again dosing equal to the orally daily maintenance dose, will be given 6 hours after the morning dose. Any patient with more than trace oedema, residual pleural effusion or residual ascites would be considered to be still volume overloaded (see Figures 2). Residual pleural effusion and/or ascites should always be confirmed by chest X-ray or echography. If pleural effusion/ascites is used as an inclusion criteria, chest X-ray and/or echography should be repeated until decongestion has been achieved (volume assessment score ≤ 1). If not present at inclusion, new evidence of pleural effusion and/or ascites may arise during the treatment phase, but if scored it should be confirmed by a chest X-ray or echography. If the patient is not volume overloaded anymore, the intravenous administration of study medication should be stopped. Once decongestion is achieved (volume assessment score ≤ 1) during the treatment phase, no volume assessment should be performed anymore the following morning.

4.3.1 STOP TREATMENT

The treating physician is allowed (but not obliged) to stop the study treatment, in case of persistent volume-overload in following cases:

- symptomatic hypotension with a systolic blood pressure <100 mmHg
- asymptomatic hypotension with a systolic blood pressure <90 mmHg
- an increase of serum Creatinine levels x 1.5 of the serum Creatinine level compared to admission value
- occurrence of metabolic acidosis (pH < 7.2)

The discontinuation of the study treatment will be seen as a failure for the primary endpoint (decongestion not achieved). However, if any of these events occur when the patient is judged to be euvolemic, the study treatment is stopped and the primary endpoint is considered to be successful (decongestion achieved).

Freedom from volume-overload (i.e. successful decongestion) on the morning of day 4 will be defined as not more than trace oedema, no residual pleural effusion, and no residual ascites (Figure 2).

4.3.2 Treatment DOSE ADJUSTMENTS in case of an inappropriate diuretic response

If the total urinary output on the morning of day 3 is < 3500 mL and the patient is still volume overloaded, an escalation of decongestive treatment is mandatory. One of the outlined three options can be chosen at the discretion of the treating physician.

Escalation therapy options:

- doubling of the IV dose of the loop diuretics
- add oral chlorthalidone 50 mg once daily
- ultrafiltration or renal replacement therapy might be considered

The decision to proceed with escalation therapy will be collected in the case report as the need for escalation implies a failure for the primary endpoint.

